Fatigability (fatigue in the context of a standardized task) will be assessed using the Pittsburgh Fatigability Scale, a 10-item scale that assesses physical and mental fatigability, with scores ranging from 0-50 (higher scores indicate greater fatigability).⁸⁸ This is an important measure to consider as individuals often “self-pace” or lower their level of activity or exertion in performing a task to reduce their fatigue.

Self-efficacy will be assessed using the Weight Efficacy Lifestyle Questionnaire (WEL), a validated, 20-item questionnaire that is sensitive to change and highly predictive of weight loss.⁸⁹⁻⁹⁹ Participants will be asked to rate their confidence in resisting the desire to eat in 5 situational domains (availability, negative emotions, physical discomfort, positive activities, and social pressure) using a 10-point scale that ranges from 0 (not confident) to 9 (very confident).¹⁰⁰ Subscales scores will be summed to yield a total self-efficacy score.

Descriptive Variables and Potential Confounders

Because this is a randomized trial, we have no *a priori* reason to expect confounding factors to be unbalanced between intervention groups. Nevertheless, the following variables will be evaluated to estimate their influence on the outcomes of interest.

Demographics and co-morbidities: Information regarding age, race/ethnicity, tobacco use, alcohol intake, socioeconomic status (i.e., education, insurance status, employment status), and co-morbidities will be ascertained at the screening visit. The Charlson comorbidity index will be used to quantify disease burden.¹⁰¹

Medication use: Participants will be asked to bring in all medications and dietary supplements for a “brown bag” review during the screening visit. Medication name and dosage will be recorded and coded using the Iowa Drug Information System (IDIS).¹⁰² Participants will be asked to inform staff of medication changes, which will be reviewed at the 3- and 6-month study visits using a structured medication inventory form.

Time to enrollment: Delay time will be defined as the number of days between hospital discharge and start of cardiac rehabilitation.

Recurrent Events

Cardiovascular events and rehospitalizations will be assessed by staff masked to group assignment. Pertinent medical records will be obtained to confirm all events and procedures. Hospitalizations will be categorized using the Clinical Classifications Software system from the Agency for Healthcare Research and Quality (<https://www.hcup-us.ahrq.gov/toolssoftware/ccs10/ccs10.jsp>). The study physician (masked to group assignment) will adjudicate each outcome using standardized criteria.

Analytical Plan

Sample Size

Assuming that at least 50% of eligible patients will be interested in participating in the study and meet the full inclusion/exclusion criteria, we anticipate enrolling 1-2 participants per week. Based on a conservative dropout rate of 20%, we expect a final sample size of 16 per group. While this pilot study is not designed to provide sufficient statistical power to detect differences in the measured outcomes, we will obtain estimates of treatment efficacy and estimate the variability of outcome measures in this population to use in the design of a larger, more definitive trial.

Data Cleaning

We will examine the distributions of the outcome variables and the need for any transformations to approximate conditional normality for further analysis. Summary statistics will be calculated, including means, standard deviations, quartiles, and ranges for continuous variables, and counts and percentages for categorical variables. Range and validation checks will be performed on all variables in collaboration with study personnel. We will examine the distributions of all the variables, identify the potential outliers and influential points, and clean any unreasonable data.

Statistical Analyses

All randomized participants will be included in their original intervention group regardless of compliance with the study protocol (i.e., an “intent to treat” analysis). Chi-square tests will be used to assess group differences in retention and compliance rates. Longitudinal data for the outcome variables will initially be presented graphically (e.g., spaghetti plot) with individual trajectories over time. The graphical displays will help to highlight aggregate patterns of potential scientific interest and identify unusual values. The mixed-model repeated measures ANCOVA model will be used to determine whether Rehab+WL leads to greater improvements in CHD and neurovascular outcomes than Rehab alone. A

subject random effect will be included to account for the fact that multiple measurements within a participant over time are not independent. Fixed effects will include sex and obesity severity (i.e., the randomization stratification factors), clinical site (WFBMC, DMC, or LMC), the baseline (pre-randomization) value, time (3 or 6 months), the group assignment, and the group by time interaction. Hypothesis tests for intervention effects at the 3- and 6-month study visits will be performed using contrasts of the 3- and 6-month intervention group means. The primary comparison will be based on an intervention contrast at 6 months. Overall comparisons between groups across follow-up visits will be obtained using a contrast to compare average effects across both follow-up visits. Associations with the stage of change (S-Weight) and P-Weight scores will be examined to determine their influence on recruitment, retention, adherence, CHD outcomes, and neurovascular outcomes. If a particular intervention group has a markedly higher dropout rate, we will attempt to identify baseline covariates that predict attrition in secondary analyses. If such covariates can be identified, the analysis of the outcome measure will adjust for those covariates. Other factors that may influence the measured responses to the interventions such as the number of comorbidities, socioeconomic status, time to enrollment, medication use, and magnitude of weight loss will also be evaluated. Differences in intervention process measures (e.g., total volume of exercise) and compliance measures (e.g., attendance at diet and exercise sessions) will also be examined to assess the extent to which these variables contribute to the outcomes.

Human Subjects Protection

Subject Recruitment Methods

Inpatient recruiting will be performed primarily via a joint effort by the study coordinator and the program manager, with supervision by the study physician ([name], Co-I) and the study PI ([name]). In addition, the Sticht Center on Aging supports a Recruitment Core service to assist investigators with targeted recruitment strategies. This service, which has successfully recruited participants for 8 weight loss trials since 1997, will also be available for the proposed study. WFBH has a systematic referral process in place to help increase access to and enrollment of eligible patients in cardiac rehabilitation. The study coordinator, with help from specially-trained nurses serving as cardiac wellness coordinators and cardiac rehabilitation staff, will assess ability and willingness to participate. Currently, 50-80 patients are referred to cardiac rehabilitation each month and 6-8 new patients start the program each week. Tapping into this automatic referral system will allow us to easily identify potential candidates for our study and interact with them early in the referral process to assess eligibility. Informational study flyers will also be included in discharge packets and letters will be mailed to patients admitted to WFBH with a CHD-related diagnosis or procedure. Significant pre-screening will be performed by review of clinic, hospital, echocardiography, and cardiac catheterization records, as well as digitally copied ECGs and other relevant diagnostic and procedure reports. Further screening using data forms specifically designed for this purpose will be conducted by telephone and in-person (on the same day as the consultation or at a separate visit, if necessary). Every effort will be made to enroll participants within 2 weeks of hospital discharge (i.e., 3 weeks after index event).

Informed Consent

Prior to any data collection, all participants must provide written informed consent to participate in the study and complete a HIPAA authorization form in accordance with the Wake Forest School of Medicine Institutional Review Board (IRB) policies. Written informed consent will be obtained by research staff after explanation of the entire protocol. Staff will explain the purpose, methods and extent of the study to prospective participants who will then be asked to read the informed consent form and ask questions. The form will be written in simple, easy to understand language. All of the key aspects of the study will be verbally reviewed. Staff will be provided with a structured checklist for this purpose. Participants will be asked specifically about the storage of blood samples for use in future studies. In order to participate in this study, they must be willing to provide blood samples for future research. At any time, participants will be able to request that their samples or data be withdrawn from current or future use by contacting

the PI. Participants will also be asked to complete a medical records release form so that study staff can adjudicate any hospitalizations and deaths that occur over the course of the study. One copy of the consent form will be placed in the participant's medical record which will be kept in a locked file and another copy will be given to the participant for his/her records.

Potential Risks

There are potential risks associated with some aspects of the proposed research study. However, the intervention procedures have been designed to minimize the danger of major complications, and all tests are performed by trained, experienced research staff who will be supervised by qualified medical personnel as needed. Risks associated with specific procedures and the interventions are discussed below.

- 1) Questionnaires: The interviews and questionnaires participants complete in this study are of minimal risk. These include the Montreal Cognitive Assessment (MoCA), 9-item Patient Health Questionnaire (PHQ-9), Medical Outcomes Study Short Form 36 (SF-36), Pittsburgh Fatigability Scale questionnaire, Weight Efficacy and Lifestyle (WEL) questionnaire, and the stages and processes of change questionnaires for weight management (S-Weight and P-Weight, respectively). Care will be taken to ensure participant privacy and confidentiality while discussing personal and health information. It is possible that some patients with previously undiagnosed mild cognitive impairment (MCI) or major depressive symptoms will be found to have these problems. Patients with MCI and major depression at screening will be excluded from further participation and referred for appropriate medical follow-up. Study participants who develop signs of mild-to-moderate depression at the follow-up visits will be referred to outpatient counseling services through CareNet. Those with moderate-to-severe depression will be referred to their primary care physician, or psychiatry if necessary, for further evaluation.
- 2) 6-Minute Walk Test: There is a slight risk of falling during this test, and occasionally participants become short of breath or fatigued and must rest and/or stop the test. To minimize risk, American Thoracic Society (ATS) guidelines will be followed for performing and stopping the test. Participants will be closely monitored during the test, including measurement of heart rate and oxygen saturation. We will also make sure that the walking path is clear and that trained staff is always nearby. We have had no serious adverse events during or after 6MW tests in over 500 middle-aged and older study participants.
- 3) Physical function tests: There is a small risk of injury during the physical function tests, such as muscle strains or pulls, falls, or joint injury. Risks will be minimized by having experienced/trained staff conducting these assessments. A warm-up and range of motion practice will be conducted before testing. If a participant reports pain, dizziness, or other medical problem, the test will be terminated.
- 4) DXA scans: Other than some exposure to radiation, there are no risks associated with the DXA scans. Participants will receive approximately 3 mrem of radiation from the whole body DXA scans (includes 1 baseline and 2 follow-up scans) over the course of 6 months. This amount is equal to 0.01 times the amount of natural background radiation that the average person in the United States receives each year (300 mrem). The potential long-term risk from this radiation is uncertain, but these doses have never been associated with any definite adverse effects. To manage this modest amount of risk, all scans will be performed and analyzed by a trained DXA technician who is certified by the International Society for Clinical Densitometry and has vast experience in body composition measurements in middle-aged and older adults.
- 5) Cardiac MRI Scans: There are no risks associated with the MRI scans. Some people may experience discomfort in the scanner if they are uncomfortable in tight places or if the noise from

the scanner bothers them. To minimize this discomfort, participants will be screened for claustrophobia and will be asked to wear earplugs.

- 6) Blood Draw: Participants may experience slight discomfort, bruising and/or bleeding where the needle is inserted. Occasionally, some people become dizzy, lightheaded, or feel faint. Infection may also occur on rare occasions. To minimize these risks, blood will be drawn only by trained and experienced phlebotomists.
- 7) Cardiac Rehabilitation: The risks associated with the prescribed aerobic and resistance exercises are minimal and include loss of balance and a risk of injury from falls while walking, fatigue, and muscle strains or sprains. Other potential risks from exercise, such as an abnormal heart rhythm, a heart attack, a stroke, or even death, are rare (less than 1 in 50,000 patient hours of exercise). To minimize the risk of injury and ensure the safety of study participants, standard procedures for exercise progression will be followed in accordance with the American College of Sports Medicine (ACSM) recommendations. The intensity of exercise will gradually increase over the first few weeks, and each session will include warm-up and cool-down activities, as well as light stretching. All exercise sessions will be supervised by exercise physiologists who are trained in advanced cardiac life support and each participant's response to exercise (heart rate, blood pressure, perceived exertion) will be closely monitored before, during, and after each session. Additionally, a fully stocked crash cart will be available with all necessary emergency equipment (drugs, defibrillator, airway management) to deal with medical emergencies. Institutional and community EMS services will also be activated if needed.
- 8) Weight Loss: The risks of caloric restriction are small and include excessive weight loss. These risks will be minimized by the direct involvement of a registered dietitian and medical oversight by the study physician. To ensure safety of study participants, food plans will be tailored to individual preferences, the lowest calorie level permitted will be 1,100 kcals for women and 1,200 kcals for men, and calorie goals will be closely monitored to minimize rapid or excessive weight loss. Weight loss interventions also have the potential to increase risk of hypoglycemia and hypotension. To minimize these risks, study staff will contact the primary care provider of any participant treated with glucose- or blood pressure-lowering medications who develops symptomatic hypoglycemia or hypotension to discuss adjustment or discontinuation of these medications. If a primary care provider cannot be contacted in a timely manner, the study physician may elect to adjust these medications and the personal care provider will be notified by phone and in writing. We have previously completed 8 weight loss trials in a variety of populations with no reports of significant adverse effects.
- 9) Neurovascular Testing: Risks and side effects related to TCD monitoring include reaction from the gel and risk of skin irritation from the TCD headband. However, these are very rare occurrences and no adverse events associated with TCD usage have been reported in the literature. The ECG electrodes may also cause some skin irritation or a mild rash; however, this usually goes away without treatment once the electrodes are removed. Some people may experience discomfort from the finger cuff squeezing their fingers. If this occurs another finger can be used for the assessment. Some fatigue during the sit-stand tests is normal and some people may feel claustrophobic when the non-rebreathing mask is placed over their nose and mouth; if this discomfort persists or if the participant experiences pain, dizziness, or other medical problem, the test will be terminated. Study staff will assess for any signs of pain or intolerance throughout the testing procedure.

Medical Clearance

The study physician and/or PI will personally review the relevant medical records to ensure inclusion/exclusion criteria are met and that it is safe for the participant to participate. Study results related to blood pressure, hemoglobin A1c, glucose, lipid, and other relevant lab values that are obtained during scheduled study visits will be provided to each participant's primary care provider in a form that clearly indicates abnormal values and ranges. When a cardiovascular event is discovered during the trial, the study physician will decide whether it is permissible for the participant to continue the intervention. If the intervention is discontinued for safety reasons, it may be resumed after consultation with the participant's primary care provider.

Medical Costs

This study will involve a partnership with the Cardiac Rehabilitation Program at WFBH. Costs to attend cardiac rehabilitation for 6 months will be provided for all study participants.

Study Incentives

Participants will be provided with \$50 for each study visit completed (\$150 total for completing all study visits). This incentive is designed to help offset the cost of traveling to/from the medical center for study-related visits and purchasing food or prepared meals in accordance with the individualized meal plans.

Confidentiality and Privacy

Confidentiality will be protected by collecting only information needed to assess study outcomes, minimizing to the fullest extent possible the collection of any information that could directly identify participants, and maintaining all study information in a secure manner. To help ensure participant privacy and confidentiality, only a unique study identifier will appear on data collection forms. Any collected patient identifying information corresponding to the unique study identifier will be maintained on a linkage file, store separately from the data. The linkage file will be kept secure, with access limited to designated study personnel. Following data collection subject identifying information will be destroyed at least six years after the study ends consistent with data validation and study design, producing an anonymous analytical data set. Data access will be limited to study staff. Data and records will be kept locked and secured, with any computer data password protected. No reference to any individual participant will appear in reports, presentations, or publications that may arise from the study.

Data and Safety Monitoring

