Patients who meet all inclusion/exclusion criteria and provide informed consent to participate will be randomized to Rehab only or Rehab+WL using a randomization scheme with blocking stratified by sex and obesity severity (BMI<30 vs. BMI≥30 kg/m²). Block size and the randomization sequences will be unknown to all other study personnel. Study staff will be able to access individual treatment assignments through the study database which will be managed in the secure, web-based application REDCap (Research Electronic Data Capture).³³

Study Interventions

Cardiac Rehabilitation

All participants will undergo standard exercise-based cardiac rehabilitation at a WFBH site which consists of three exercise sessions and one group health/nutrition education class per week for 12 weeks.³⁴ Participants also have one meeting with a dietitian, usually within the first 2 weeks of the program, to discuss dietary concerns and address issues noted in the dietary assessment. In order to provide sufficient time for adequate weight loss and ensure the necessary behavioral adaptations for long-term maintenance of lifestyle changes, all participants will undergo an additional 12 weeks of supervised cardiac rehabilitation for a total period of 6 months. Cardiac rehabilitation will be conducted by program staff (including exercise physiologists, nurses, and dietitians) with many years of experience in risk factor management and exercise prescription.

Exercise: Each exercise session lasts for 60 to 90 minutes and consists of 5-10 minutes of warm-up and cool-down activity; up to 30 minutes of aerobic exercise using a variety of modalities (e.g., walking laps on a track, cycle ergometry, treadmills, stair climbers); and 15-20 minutes of upper and lower body resistance exercises using Thera-Bands. An exercise physiologist creates an individualized plan based on

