As described above, the screening visit will take place on the same day as the standard cardiac rehabilitation consultation or on a separate day, if necessary. After obtaining informed consent, information collected on the patient's medical history, height, weight, and dietary habits will be reviewed by the study coordinator, and patients will be asked to complete the MoCA to confirm eligibility. Patients will also be allowed to sample the shakes and bars that will be used in the study.

The baseline visit will take place at WFBMC in the morning after an 8-hour overnight fast within approximately 1 week following the screening visit. Participants will have their weight and blood pressure measured and will undergo tests to assess arterial stiffness, including carotid-femoral pulse wave velocity (PWV), aortic augmentation index (AIx) and arterial wave reflection magnitude. Blood will be drawn for glucose, insulin, hemoglobin A1c, lipids, complete metabolic panel, complete blood count, cardiac biomarkers, and storage. Following all fasting measures, participants will be given a snack. Medical history and current medications and dietary supplements will be reviewed. Participants will complete the 6MW test and tests of physical function, including the expanded short physical performance battery (SPPB), grip strength, and the Mobility Assessment Tool-short form (MAT-sf). A whole-body DXA scan will be done to assess body composition. Cardiac MRI scans will be conducted in participants who consented prior to July 1, 2019. Participants will have anthropometric measurements taken at their waist, hip, and thigh. The Short Form 36 (SF-36), Pittsburgh Fatigability Scale, Weight Efficacy Lifestyle (WEL), S-Weight, and P-Weight questionnaires will be administered. Sedentary behavior and physical activity will be assessed using the ActivPAL® thigh monitor. Participants will be asked to wear the device continuously for seven consecutive days. Participants will be asked to answer questions as accurately as possible about their activity and monitor use in a daily log for all of the seven days. After completion of all baseline measures, participants will be told which intervention group they have been assigned to.

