Feasibility will be assessed in terms of the ability to 1) recruit study participants (i.e., total number randomized divided by total number eligible); 2) retain participants in the study for the full 6 months (i.e., the proportion of randomized participants who return for follow-up testing); and 3) obtain adequate compliance to the prescribed intervention (i.e., total number of exercise/counseling sessions attended divided by total number of sessions prescribed). We anticipate that at least half of the eligible participants will agree to participate and of those who do, <20% will drop out prior to the study end. We also expect to achieve a compliance rate of $\geq 80\%$.

Secondary Outcomes

Body weight will be measured using a digital scale. Additional measures of body size/habitus will also be obtained, including height (using a standard wall-mounted stadiometer).

The ***6MW test*** is a valid and reproducible measure of submaximal exercise capacity that reflects the level at which most activities of daily living are performed, predicts clinical events in cardiac patients, and is therefore a clinically meaningful outcome in cardiac rehabilitation studies.⁴²⁻⁴⁴ Participants will be asked to walk at their own maximal pace on an established course, covering as much ground as they can during the allotted time, without running.^{45,46} Performance will be measured by the total distance covered in feet. Blood pressure, oxygen saturation, and HR will be measured before, during, and/or after the test.

Physical function will be assessed using 2 performance-based measures and 1 self-report measure. The expanded Short Physical Performance Battery (**SPPB**) is a modified version of a widely used assessment of lower extremity physical function that consists of 3 standing balance tasks held for 10 seconds each (side-by-side, tandem and semi-tandem), two 4-m walk tests to assess usual gait speed, and 5 repeated chair stands. To minimize ceiling effects and maximize overall dispersion of test scores, the expanded SPPB increases the holding time of the semi- and full-tandem stands to 30 seconds and adds a single leg stand and a narrow walk test of balance (walking at usual pace within lines of tape spaced 20 cm apart). Expanded SPPB scores are continuous and range from 0 to 4, with higher scores indicative of better performance.⁴⁷ **Grip strength** will be measured twice in each hand using an isometric hydraulic hand

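### Do the two statements that at least half of eligible patients will join give the recruitment outcome two different expected values?

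*Combined protocol and SAP*

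**What the plan says.** The Primary Outcome section (under Outcome Measures) defines recruitment feasibility as the ability to "recruit study participants (i.e., total number randomized divided by total number eligible". It then expects that "at least half of the eligible participants will agree to participate and of those who do, <20% will drop out" before the study ends. Retention, in the same paragraph, is a proportion of randomized participants.

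The Sample Size section (under Analytical Plan) assumes that "at least 50% of eligible patients will be interested in participating in the study and meet the full inclusion/exclusion criteria", and on that basis forecasts 1-2 enrolled per week.

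Four other places bear on what eligible means:

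- **Randomization** requires both conditions: "Patients who meet all inclusion/exclusion criteria and provide informed consent to participate will be randomized".
- **Recruitment and Screening** and **Organization of Study Visits** place the cognitive test after consent: "patients will be asked to complete the MoCA to confirm eligibility". Table 1 also lists the PHQ-9 at the screening visit.
- **Potential Risks** allows that such problems may come to light, and then "Patients with MCI and major depression at screening will be excluded from further participation and referred for appropriate medical follow-up".
- **Subject Recruitment Methods** has staff approach referred patients so as to "interact with them early in the referral process to assess eligibility", with record review and telephone screening on dedicated forms.

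**The concern.** A patient who is fully eligible already meets the full criteria. The Sample Size wording therefore makes sense only if eligible there means a preliminary stage. The Primary Outcome section names no stage. Its expectation is about agreeing, while its formula is about being randomized. Between the two lie the patients who consent and are then excluded on the MoCA or PHQ-9.

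If there are such patients, one set of screening data could show half agreeing while fewer than half are randomized. Recruitment feasibility is part of the Primary Aim, and the pilot is meant to inform a larger trial. A rate whose denominator is unclear could mislead whoever plans screening volume from it.

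**Working it through.** **The plan's own figure.** Inputs from Objectives and Sample Size: 40 randomized, 20% dropout, two groups (equal allocation, as the stated result implies). Completers per group = 40 × (1 − 0.20) / 2 = 16, which matches the stated 16. The 50% does not enter this calculation. The 50% itself is an assumption without a derivation, so there is nothing to reproduce.

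**Setting up the comparison.** Call a patient pre-eligible if he or she meets every criterion that can be checked before consent. Let *a* be the share of pre-eligible patients who consent, and *q* the share of those who then fail screening. Then

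randomized / pre-eligible = *a*(1 − *q*).

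The protocol does not give *q*. The range of 5% to 30% below is an assumption; *q* = 0 is the case of no post-consent failures.

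**Reading 1: agreeing means entering the trial.** Both sections then say *a*(1 − *q*) ≥ 0.5. They coincide for any *q*, and 40 randomized needs at most 40 / 0.5 = 80 pre-eligible patients.

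**Reading 2: agreeing means consenting only.** The Primary Outcome section says *a* ≥ 0.5, and the Sample Size section says *a*(1 − *q*) ≥ 0.5.

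| *q* (assumed) | Randomized/eligible if half consent: 0.5(1 − *q*) | Consent share needed for a ratio of 50%: 0.5/(1 − *q*) | Pre-eligible for 40 randomized if half consent: 40/[0.5(1 − *q*)] |
|---|---|---|---|
| 0% | 50% | 50% | 80 |
| 5% | 47.5% | 52.6% | 84.2 (85) |
| 10% | 45% | 55.6% | 88.9 (89) |
| 20% | 40% | 62.5% | 100 |
| 30% | 35% | 71.4% | 114.3 (115) |

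The bounds are nested. If *a*(1 − *q*) ≥ 0.5, then *a* ≥ 0.5/(1 − *q*) ≥ 0.5, so meeting the Sample Size expectation always meets the Primary Outcome one. The reverse can fail. With 80 pre-eligible and *q* = 20%, 40 consent, 8 fail and 32 are randomized: agreement is 40/80 = 50% and the outcome is 32/80 = 40%.

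**Reading 3: eligible in the Primary Outcome section means fully eligible.** Agreeing is then the same as being randomized, and that section's ratio is at least 50% whatever *q* is. In the example, if decliners would have failed at the same 20% rate, 80 × 0.8 = 64 are fully eligible and 32/64 = 50%. That extra assumption cannot be checked, because decliners never take the MoCA.

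**Which reading fits the text.** The Primary Outcome section writes its ratio with randomized in the numerator. It applies dropout to those who agree, although dropout there concerns randomized participants. Agreeing is shorthand for joining, as in Reading 1. The fully eligible denominator of Reading 3 cannot be counted for decliners, which leaves the pre-eligible one, as the Sample Size section implies.

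**What rests on the 50%.** Only the accrual forecast. At 50%, 1-2 enrolled per week means 1/0.5 = 2 to 2/0.5 = 4 eligible per week, and 40 participants take 40/2 = 20 to 40/1 = 40 weeks. The forecast follows the wording that is already net of failed screening, so it uses the right quantity.

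**The case for a change.** The strongest argument for a change is that compatible lower bounds do not settle the matter. On the literal wording, data can meet one expectation and miss the other, as the 80-patient example shows. Reading agreement as randomization is an inference, since the sentence does not say it. For a trial whose Primary Aim is feasibility, the denominator of the recruitment rate deserves an explicit definition, and the cost is a line of text.

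Part of this stands. The Primary Outcome section does not tie eligibility to a screening stage, and the two sections describe the expectation in different words. The example is arithmetically right under Reading 2.

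It does not show that the plan gives two expected values. Both sections state the same figure as a minimum, and every gap in the table comes from an assumed *q*. The protocol gives no support for the upper part of that range. Inpatient screening and the coordinator's review of the criteria come before the screening visit is scheduled, and records are pre-screened. The MoCA and PHQ-9 are the only clear post-consent sources of failure, and Potential Risks presents them as possible findings, without a forecast of how many. Nor would missing an anticipated 50% trigger anything.

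**Conclusion.** The concern identifies loose wording but no conflict that calls for a change to the plan. The formula is stated, both expectations are minimums of one half, and they agree when agreeing to participate is read as entering the trial. The difference is zero on that reading. On the literal reading it is 2.5 to 15 percentage points (50% against 47.5% to 35%), but only for assumed post-consent failure shares of 5% to 30%.

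The 50% is an anticipation, with no threshold or go/no-go rule attached. The 40 randomized, the 16 per group and the treatment-effect analyses are the same on every reading. The gap is one that analysts fill sensibly: decliners are never tested after consent, so the countable denominator is patients who met the criteria checkable before consent, with refusers included. The planned screening records and forms are a natural source for that count.

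This conclusion rests on two points: that screening is documented as Subject Recruitment Methods describes, and that the 50% stays an expectation and is not later used as a pass mark.
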